9.3.4.1. Laboratory Parameters

Laboratory results (hematology, chemistry and coagulation parameters) will be graded according to NCI CTCAE, Version 5.0 (or higher). Laboratory results not corresponding to an NCI CTCAE term will not be graded. Incidences of laboratory abnormalities will be summarized with descriptive statistics.

Shift tables will be generated to display changes from baseline to the worst value on study and last value on study using values provided by the local laboratory.

All laboratory data will be included in listings and abnormal results will be flagged.

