11.5.4. Physical Examination

A listing of Physical Examination results will be provided.

11.5.5. 12-lead ECG

ECG parameters will be summarized using descriptive statistics both in terms of absolute values and change from baseline at each visit and time point.

The following parameters will be presented in the summary tables:

- Heart Rate (bpm)
- PR Interval (msec)
- QRS Duration (msec)
- QT Interval (msec)
- QTcF Interval (msec)

In addition, the following categorical analysis on QTcF interval prolongation will be presented according to the ICH E14 guideline:

- Number (%) of subjects with QTcF > 450 msec and ≤480 msec
- Number (%) of subjects with QTcF > 480 msec and ≤500 msec
- Number (%) of subjects with QTcF > 500 msec
- Number (%) of subjects with QTcF change from baseline > 30 msec and ≤60 msec
- Number (%) of subjects with QTcF change from baseline > 60 msec

Overall ECG Interpretation (Normal, Abnormal NCS, Abnormal CS) will only be listed.

All ECG parameters will be listed.

Results from unscheduled visits will not be included in the summary tables but will only be listed.

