11.5.7. Safety laboratory tests

Laboratory parameters, including haematology, chemistry and coagulation, will be summarized using descriptive statistics both in terms of absolute values and change from baseline at each visit.

Laboratory values will be reported in SI units and will be compared to the relevant reference range in SI units and categorized as follows:

- Low: < lower limit of the reference range
- Normal: \geq lower limit of the reference range and \leq upper limit of the reference range
- High: > upper limit of the reference range.

Shift tables of laboratory parameters from baseline to the worst post-baseline low/normal/high categorization will be performed; in the shift tables, percentages will be calculated based on the number of subjects that have valid data for both baseline and at least 1 post-baseline assessment.

For analysis purposes, values preceded by a “<” or “>” sign will be considered equal to the lower or upper limit of quantification, respectively.

All laboratory parameters, including low/normal/high categorization, will be listed.

Results from unscheduled visits will not be included in the summary tables but will only be listed.

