11.5.8. ECOG Performance Status

ECOG PS will be summarized using frequency counts and percentages at each visit.

In addition, shift tables of ECOG PS values from screening to End of Treatment visit will be presented.

All ECOG PS values will also be listed.

Results from unscheduled visits will not be included in the summary tables but will only be listed.

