[Table 14.3.5.3: Hematology by Visit](#)

[Table 14.3.5.4: Blood Chemistry by Visit](#)

[Table 14.3.5.5: Coagulation by Visit](#)

[Table 14.3.5.6: Hematology – Shift to Worst Post-Baseline Category](#)

[Table 14.3.5.7: Blood Chemistry – Shift to Worst Post-Baseline Category](#)

[Table 14.3.5.8: Coagulation – Shift to Worst Post-Baseline Category](#)

[Table 14.3.5.9: ECOG Performance Status](#)

[Table 14.3.5.10: ECOG Performance Status – Shift to Worst Post-Baseline Value](#)

Table 14.3.5.11: Echocardiogram**Table 14.2.1: Best Overall Response and Objective Response – Investigator's Assessment (RECIST v1.1)****Table 14.2.2: Duration of Response - Investigator's Assessment (RECIST v1.1)****Table 14.2.4: Duration of Complete Response - Investigator's Assessment (RECIST v1.1)****Table 14.2.6: Progression-free Survival - Investigator's Assessment (RECIST v1.1)****Table 14.2.8: Overall Survival - Investigator's Assessment (RECIST v1.1)****Table 14.4.1: SL-901 Plasma PK Concentrations by Cohort, Visit and Nominal Time****Table 14.4.8: SL-901 Plasma PK Parameters by Cohort and Visit**

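### As worded, the SAP keeps unscheduled results out of the worst-value lab shifts and QTcF categories, and it drops several protocol safety tables without declaring the change

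*SAP*

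**What the plan says.** SAP 11.5.7 first plans descriptive statistics for laboratory values and changes from baseline at each visit. It then adds a second output: "Shift tables of laboratory parameters from baseline to the worst post-baseline low/normal/high categorization will be performed". The index in SAP 13.2.1 titles these tables (14.3.5.6 to 14.3.5.8) "Shift to Worst Post-Baseline Category". The section closes with "Results from unscheduled visits will not be included in the summary tables but will only be listed".

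SAP 11.5.5 follows the same order: by-visit ECG summaries, then "the following categorical analysis on QTcF interval prolongation will be presented" with three bands for absolute QTcF and two for change from baseline, and the same closing sentence.

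For laboratory data, Protocol 9.3.4.1 asks for CTCAE grading where a term exists, and states: "Shift tables will be generated to display changes from baseline to the worst value on study and last value on study". It sets no limit to scheduled visits. SAP 6.3.3 applies CTCAE to adverse events only.

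The protocol also plans an over-time summary and an abnormal-value table for vital signs and weight (9.3.4.2), frequency tables for physical examination (9.3.4.4), and the proportion of patients with treatment-emergent clinically significant ECG abnormalities (9.3.7). SAP 11.5.3, 11.5.4 and 11.5.5 provide listings for these. SAP 3.1, the section for changes from the protocol, names one change: the DLT population.

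**The concern.** Unscheduled tests are often ordered because something looks wrong, so they can hold a patient's most extreme value. A worst-value table that leaves them out may not show the worst value. Abnormalities in laboratory tests, vital signs and physical examination, and ECG findings, are primary safety endpoints (SAP 5.4.1), so these tables are part of how a primary objective is reported.

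The loss of grade is a second, independent weakness. Three categories against a reference range cannot show worsening within High or within Low, and patients may enter with values already outside the range. Third, a reader who relies on SAP 3.1 to learn what differs from the protocol would not learn that these outputs have gone.

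**Working it through.** No sample-size or error-rate figure is involved. The check is a comparison of texts and a count.

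**Step 1. Reach of the unscheduled-visit rule.** Tables 14.3.5.1 to 14.3.5.11 in the SAP index divide as follows.

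| Tables | Content | Titled by visit? |
|---|---|---|
| 14.3.5.1, .3, .4, .5 | ECG, hematology, chemistry, coagulation | Yes |
| 14.3.5.2 | QTcF categories | No |
| 14.3.5.6, .7, .8 | Laboratory shifts to worst category | No |
| 14.3.5.9, .10 | ECOG status and shift | No |
| 14.3.5.11 | Screening echocardiogram | No |

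Count: 4 + 1 + 3 + 2 + 1 = 11. For ECG and laboratory data, leaving unscheduled results out of the first row is ordinary practice. The literal wording also reaches 1 + 3 = 4 tables that are not by visit: 14.3.5.2, .6, .7 and .8.

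**Step 2. Where an extreme laboratory value would appear.** Protocol 5.2 admits AST/ALT up to 2.5 x ULN. Assume, for illustration only, entry at 2 x ULN and a rise to 10 x ULN (10 / 2 = five-fold).

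| Case | Worst-category shift, literal rule | Worst-category shift, all results used | By-visit table |
|---|---|---|---|
| Normal at baseline, High only at an unscheduled visit | High value not counted | Normal to High | Not shown |
| 2 to 10 x ULN at a scheduled visit | High to High | High to High | In that visit's maximum and change from baseline |
| 2 to 10 x ULN, the 10 x ULN value only at an unscheduled visit | High to High | High to High | Not shown |

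In every case the value is listed, and it enters the graded AE tables if the Investigator reports it as an AE. The first row is the effect of the unscheduled rule. The other two show that clarifying that rule would not recover severity; only grading does.

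QTcF works like the first row. A reading above 500 msec, or a rise above 60 msec, seen only at an unscheduled ECG would enter no band on its own account under the literal rule.

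**Step 3. Protocol outputs against SAP outputs.**

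| Protocol section | Protocol output | SAP output | In SAP 3.1? |
|---|---|---|---|
| 9.3.4.1 Laboratory | CTCAE grade; shifts to worst and last value | Low/normal/high; shift to worst category only | No |
| 9.3.4.2 Vital signs, weight | Summary over time; abnormal values tabulated | Listing (11.5.3) | No |
| 9.3.4.4 Physical examination | Frequency tables | Listing (11.5.4) | No |
| 9.3.7 ECG | Proportion with clinically significant abnormalities | Interpretation listed (11.5.5) | No |

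Sections reduced: 4. Declared: 0. None of the 11 tables in Step 1 shows laboratory CTCAE grade, a last-value laboratory shift, vital signs, physical examination or ECG interpretation. SAP 11.5.1 adds to the tension: it says physical examination and vital signs will be presented by cohort and overall, whereas 11.5.3 and 11.5.4 give listings.

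**The case against.** The best answer is that the rule was meant for the by-visit tables alone. Both sections describe by-visit summaries and then introduce the shifts or categories as separate items. The index keeps that split: only 14.3.5.1 and 14.3.5.3 to 14.3.5.5 carry a by-visit title. The denominator for the shift tables needs a baseline and at least one post-baseline value, with no mention of scheduled visits. This reading is plausible. It is not stated, however, and a rule that unscheduled results are only listed contradicts it. A programmer following the words would exclude them.

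On QTcF, the SAP does not say in its own text which post-baseline value decides the band. It cites ICH E14, which is not among the documents, so whether that reference settles the point cannot be judged here. The protocol planned these categories only if warranted, so the SAP otherwise goes further than it had to.

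On laboratory data, a reader might infer that a large rise within High is invisible. It is not. At a scheduled visit it appears in the by-visit maximum and change from baseline, and planned cohorts of 3 to 6 patients per schedule make it easy to find. What is missing is a count of patients by grade. The protocol does not ask for shifts by grade and direction, so those remain optional.

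On disclosure, Protocol 9.4 sends changes of method to the study report. Silence in SAP 3.1 is therefore a documentation gap and not a breach of the protocol.

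**Conclusion.** The point holds as a wording fault with a real consequence if followed literally, plus four undeclared reductions in safety output. It should be corrected, but its weight is moderate. The size that can be shown is 4 tables under the literal rule, and 4 protocol sections with 0 declared. The number of patients affected cannot be estimated, because the documents give no frequency of unscheduled tests.

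The consequence is limited. All values are listed, clinically significant worsening after the first dose is reportable as an AE (Protocol 8.1.4 and 8.3), safety was reviewed at weekly cohort meetings (SAP 7.4.1), and Part 1b was not started. Escalation decisions do not depend on these tables.

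Two stronger readings are not supported. One is that the SAP is known to exclude worst values: that depends on which of two readings was intended. The other is that Table 8 of the protocol, whose ECGs after the Cycle 1 Day 15 series are all predose, measures how much QTcF information is lost. That describes the ECG schedule and not the effect of the rule, and the Schedule of Assessments is not visible, so other scheduled ECGs cannot be ruled out.

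The comparison assumes that protocol version 3.0, the version supplied, governs. The SAP cites version 2.0 and subsequent amendments.

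**What to change.** 1. In SAP 11.5.5 and 11.5.7, limit the exclusion of unscheduled results to Tables 14.3.5.1 and 14.3.5.3 to 14.3.5.5. State that Tables 14.3.5.2 and 14.3.5.6 to 14.3.5.8 use all post-baseline results, scheduled and unscheduled, and that each patient's highest QTcF and largest increase from baseline decide the bands.
2. Tabulate laboratory results by CTCAE grade where a term exists, and add the shift to the last value, as Protocol 9.3.4.1 requires. Keep low/normal/high for parameters without a CTCAE term. Separate shifts for low and high direction would help for two-sided parameters such as potassium, but are optional.
3. Restore the vital-sign and weight tables, the physical-examination frequency table and the proportion with clinically significant ECG abnormalities, or declare each omission in SAP 3.1 and in the study report. Bring SAP 11.5.1 into line.
4. As a separate editorial matter, reconcile SAP 11.5.8, where "shift tables of ECOG PS values from screening to End of Treatment visit will be presented", with Table 14.3.5.10, titled "Shift to Worst Post-Baseline Value".

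The cost is a short SAP revision and minor reprogramming of descriptive tables from data already collected and listed. Reported abnormality counts may rise.

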11.5.8. ECOG Performance Status

ECOG PS will be summarized using frequency counts and percentages at each visit.

In addition, shift tables of ECOG PS values from screening to End of Treatment visit will be presented.

All ECOG PS values will also be listed.

Results from unscheduled visits will not be included in the summary tables but will only be listed.

11.5.9. Reproductive System Findings and Pregnancy Test

Reproductive system findings (child-bearing potential, postmenopausal status, surgical sterilization) as well as pregnancy test results (positive/negative) at each study visit will only be listed.

11.5.10. Treatment exposure and compliance

The following parameters will be summarized using descriptive statistics:

- Cumulative dose (mg) is the sum of the number of capsules taken at each occasion multiplied by the strength of each capsule.
- Treatment duration from first intake (days) is calculated as (Last dose date – First dose date in run-in period + 1).
- Treatment duration from Cycle 1 Day 1 (days) is calculated as (Last dose date – First dose date in Cycle 1 Day 1 + 1).
- Actual Dose Intensity (mg/day) = [cumulative dose (mg)] / [treatment duration from first intake (days)]
- Planned Dose Intensity (mg/day) = Total daily dose for the cohort (see Table 1).
- Relative Dose Intensity (%) = [actual dose intensity (mg/day)] / [planned dose intensity (mg/day)]

Study treatment administration at the site and study drug accountability as collected in the eCRF, as well as the daily records from the patient diary will be listed.

12. Efficacy evaluations

Efficacy evaluations are based upon the Investigator's assessment.

Tumor assessment will occur at Screening (for identification of baseline disease) and after every 2 cycles of treatment thereafter. Response will be evaluated using Response Evaluation Criteria in Solid Tumors (RECIST) v1.1.

After completion of the EOT visit, patients will then be followed every 90 days for survival status for 12 months. The survival follow-up may be by telephone contact. If the patient discontinued study drug for reasons other than progressive disease, disease assessments should continue to be performed on an every 8-week basis (± 1 week) through 6 months after the first study drug dose and then on an every 90-day basis or until, in the judgment of the Investigator, there is evidence of relapsed or progressive disease.

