6.6.1. Intra-Patient Dose-Escalation

Intra-patient dose escalation to the MTD may be considered for patients who, at the time the MTD is determined, have experienced a confirmed objective response or stable disease for at least 4 treatment cycles with SL-901; AND have not experienced any \geq Grade 3 toxicity that was considered by the Investigator to be related to SL-901; AND do not exhibit any evidence of cumulative toxicity that can be considered related to SL-901.

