8.8. Pharmacokinetics

See [Table 8](#) for the PK assessment schedule.

A large black rectangular box redacting content from the original document.

8.9. **Electrocardiogram**

Twelve-lead ECGs will be performed 5 to 10 minutes before the PK sample is collected and analyzed locally in triplicate over 5 minutes (\pm 5 minutes) contemporaneously with selected PK sampling time points, as indicated in [Table 8](#).

Table 8: Time Points for Pharmacokinetic and Electrocardiogram Assessments

Timepoint	Run-in Serial PK Sampling and ECGs (3-7 days before C1D1; Part 1a only)		Steady State Sampling and ECGs (C1D8; C1D22; C2D1; C2D8; C2D15; C2D22; Cycles 3 and beyond D1, D15 Part 1a and Part 1b)		Serial PK Sampling and ECGs (C1D15 Part 1a and Part 1b)	
	PK	ECG¹	PK	ECG¹	PK	ECG¹
Predose	X	X	X	X	X	X
60 minutes postdose	X	X	--	--	X	X
2 hours postdose	X	X	--	--	X	X
4 hours postdose	X	X	--	--	X	--
6 hours postdose	X	--	--	--	X	--
8 hours postdose	X	--	--	--	X	--
10 hours postdose	X	--	--	--	X	--
12 hours postdose	X	--	--	--	X	--
24 hours postdose	X	X	--	--	X	X
48 hours postdose	X	X	--	--	--	--
72 hours postdose	X	X	--	--	--	--

C = cycle, D = day, ECG = electrocardiogram, PK = pharmacokinetic

¹. ECG should be performed as triplicates and at least 5-10 minutes before the PK sample is collected.

8.10. **Pharmacodynamics**

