5.2. Schematic study design

Screening assessments are performed subsequent to the patient providing an informed consent and within 28 days before the first administration of SL-901 at the Run-in PK sampling day, unless otherwise specified.

In both study parts a treatment cycle is considered to be 28 days, with daily dosing throughout the cycle.

All patients will receive SL-901 as a single agent in an open-label fashion; study drug will be dispensed to patients at scheduled study center visits on a per-cycle basis. SL-901 capsules (20 mg and 60 mg) are packaged into 50-cc high-density polyethylene (HDPE) bottles, 14 capsules per bottle.

Tumor assessment will occur at Screening (for identification of baseline disease) and every 2 cycles of treatment thereafter. Response will be evaluated using Response Evaluation Criteria in Solid Tumors (RECIST) v1.1.

[figure not shown]
In Part 1a, a serially sampled PK profile will be obtained for a single dose (Run-in PK sampling) and at steady-state (C1D15); in Part 1b, the PK sample collection schedule will be informed by data collected in Part 1a.

[figure not shown]
All Serious Adverse Events (SAEs) and non-SAEs will be recorded in the study's clinical database from the day of informed consent signature (SAEs) or from the day of first exposure to SL-901 (AEs) through 30 days after the last dose of SL-901.

[figure not shown]
After completion of the End of Treatment (EOT) visit, patients will then be followed every 90 days for survival status for 12 months. The survival follow-up may be by telephone contact. If the patient discontinued study drug for reasons other than progressive disease, disease assessments should continue to be performed on an every 8-week basis (± 1 week) through 6 months after the first study drug dose and then on an every 90-day basis or until, in the judgment of the Investigator, there is evidence of relapsed or progressive disease.

[figure not shown]

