7.3. Analysis populations

The following analysis populations will be considered in the statistical analysis:

- DLT population: All patients receiving the complete run-in dose and at least 75% of the planned SL-901 doses in Cycle 1 and completing study assessments through C2D1, or patients discontinuing Cycle 1 due to DLT irrespective of the SL-901 dose actually received.
- Safety population: all patients enrolled into the study and who received any amount of SL-901.
- Efficacy population: all patients enrolled into the study and who received any amount of SL-901 (it corresponds to the safety population).
- Per Protocol (PP) population: all patients who received at least 1 cycle of treatment, have at least 1 post-baseline efficacy assessment, and have no major protocol violations.
- PK population: all patients who receive at least one dose of SL-901 and have at least one PK sample collected and the corresponding PK concentration. .

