min [max(PD date + 1, last SL-901 dose date + 1), end date of new anti-cancer therapy].

Last study drug administration

The following rules should be used for the imputation of date of last SL-901 administration:

- If the date of last administration is completely missing and there is no EOT eCRF and no death date, the subject is considered as ongoing and the cut-off date should be used as the last dosing date.
- If the date of last administration is completely or partially missing and the EOT eCRF is available (prior to any death date or withdrawal of consent date, if available):
 - Case 1: The date of last administration is completely missing, and the EOT visit date is complete, then this latter date should be used.
 - Case 2: Only Year(yyyy) of the dose end date is available and yyyy < the year of EOT date:
Use Dec31yyyy
 - Case 3: Only Year(yyyy) of the dose end date is available and yyyy = the year of EOT date:
Use EOT date
 - Case 4: Both Year(yyyy) and Month (mm) are available for the date of last administration, and yyyy = the year of EOT date and mm < the month of EOT visit: Use the last day of the Month (mm).
 - Use min (EOT date, death date) for all other cases.

After imputation, compare the imputed date with the start date of that specific record, if the imputed date is < start date of that record: Use the start date of that record.

Tumor Assessment

Completely or partially missing Tumor Assessment (TA) dates will not be imputed.

- In case date of last TA is missing and there are no previous TA dates, then the date of first study drug admin will be used for censoring

- In case date of last TA is missing and there are previous TA dates, then the previous TA date will be used for censoring
- If there are multiple scan dates associated with an evaluation, the earliest of the scan dates associated with the evaluation will be used as the date of assessment.

Handling of PK concentrations Below the Lower Limit of Quantification and missing sampling timepoints

In all data presentations (except listings), plasma concentration values below the lower limit of quantification (BLQ) will be set to zero before the t_{max} and to “missing” after the t_{max} . Data-replacements will be implemented by the PK analyst from Clinical Pharmacology and Pharmacometrics department.

In listings, BLQ values will be reported as “BLQ”.

A footnote will be added to the listing, tables, and figures, to indicate the lower limit of quantification (LOQ) value.

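### Relative dose intensity counts the PK run-in gap as missed drug, so a fully compliant once-daily patient on the cohort dose scores 82.9% to 93.5% after one cycle

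*SAP*

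**What the plan says.** SAP 11.5.10 sets out the exposure measures. Cumulative dose sums all capsules taken, so it includes the run-in dose. The numerator and denominator of dose intensity are then fixed by "Actual Dose Intensity (mg/day) = [cumulative dose (mg)] / [treatment duration from first intake (days"), and that duration starts at the run-in dose and counts both end days. The comparator is "Planned Dose Intensity (mg/day) = Total daily dose for the cohort (see Table 1"). Relative dose intensity (RDI) is the first divided by the second. The same section has a second duration, introduced by "Treatment duration from Cycle 1 Day 1 (days) is calculated as" and starting at Cycle 1 Day 1 (C1D1), but neither intensity formula uses it.

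The timing of the run-in comes from Protocol Table 8: "Run-in Serial PK Sampling and ECGs (3-7 days before C1D1; Part 1a only"). SAP 5.2 says that "a serially sampled PK profile will be obtained for a single dose (Run-in PK sampling"), and the DLT population in SAP 7.3 treats the run-in dose as separate from the Cycle 1 doses: "All patients receiving the complete run-in dose and at least 75% of the planned SL-901 doses in Cycle 1".

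Two further provisions bear on the result. Protocol 6.6.1 allows some patients to go above their cohort dose: "Intra-patient dose escalation to the MTD may be considered for patients who" meet its conditions. SAP 11.3 imputes a missing last-dose date from the End-of-Treatment (EOT) visit: "Case 1: The date of last administration is completely missing, and the EOT visit date is complete, then this latter date should be used". Case 3 of that list does the same when only the year is known and matches the EOT year. The closing fallback takes the earlier of the EOT and death dates.

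**The concern.** The two halves of the ratio describe different schedules. The actual side spreads the dose over every day since the run-in intake. The planned side assumes a full daily dose on each of those days, including the days between the run-in dose and C1D1 when none appears to be scheduled. A patient who follows the protocol exactly and stays on the cohort dose cannot reach 100%.

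The shortfall depends on run-in length and time on treatment, not on compliance. It is largest in patients who stop early. The run-in belongs to Part 1a only and Part 1b was not started, so the formula affects the whole treated population. Results are shown by cohort, with 3 to 6 patients planned in each, so one patient's run-in length can move a cohort mean.

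**Working it through.** The documents state no RDI value, so there is no figure to reproduce. The check applies the SAP formulas to a patient who takes every scheduled dose.

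**Inputs**
- Run-in dose *k* days before C1D1, *k* = 3 to 7 (Protocol Table 8).
- One dose in the run-in (SAP 5.2).
- 28-day cycles with dosing every day (Protocol 4.1.1), and no dose modification in the run-in or Cycle 1 (Protocol 7.2).
- *D* = cohort total daily dose; *d* = days from C1D1 to the last dose, inclusive.
- *r* = run-in dose as a fraction of *D*. For QD, *r* = 1. For BID the documents do not say whether the run-in is one unit dose (*r* = 0.5) or the full daily dose (*r* = 1).

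**Formula**
- Cumulative dose = (*d* + *r*)·*D*
- Duration from first intake = *d* + *k*
- RDI = (*d* + *r*)/(*d* + *k*)

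**Fully compliant, kept on the cohort dose**

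| Time on treatment | *k* = 3 | *k* = 7 |
|---|---|---|
| QD, 1 cycle | 29/31 = 93.5% | 29/35 = 82.9% |
| QD, 2 cycles | 57/59 = 96.6% | 57/63 = 90.5% |
| QD, 4 cycles | 113/115 = 98.3% | 113/119 = 95.0% |
| QD, 6 cycles | 169/171 = 98.8% | 169/175 = 96.6% |
| BID, *r* = 0.5, 1 cycle | 28.5/31 = 91.9% | 28.5/35 = 81.4% |
| BID, *r* = 0.5, 6 cycles | 168.5/171 = 98.5% | 168.5/175 = 96.3% |

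If BID patients take the full daily dose at run-in, the QD rows apply to them too.

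**What this looks like**
- After one cycle the QD shortfall resembles 28 × (1 − 29/31) = 1.8 to 28 × (1 − 29/35) = 4.8 missed doses out of 28.
- Two fully compliant QD patients with run-ins of 3 and 7 days differ by 93.5 − 82.9 = 10.6 points. In a cohort of three that moves the mean by about 10.6/3 = 3.5 points.
- A QD patient who took 25 of 28 Cycle 1 doses (89.3%), the last on Day 28, shows 26/31 = 83.9% with a 3-day run-in and 26/35 = 74.3% with a 7-day run-in.
- A QD patient who took only the run-in dose has a duration of 1 day and scores 1/1 = 100%, above every patient in the table.

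**After the change.** With dose and duration both counted from C1D1, the fully compliant patient scores *d*/*d* = 100% for any *k*.

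**Last-dose imputation.** Protocol 7.3 places the EOT visit 30 (±3) days after the last dose. A last-dose date set to an on-schedule EOT visit is therefore 27 to 33 days late. For a fully compliant QD patient after two cycles with a 3-day run-in, a 30-day overrun takes RDI from 57/59 = 96.6% to 57/89 = 64.0%. Counting from C1D1 does not cure this: 56/86 = 65.1%.

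**The case against.** The strongest reply concerns weight. RDI feeds no threshold, population, decision rule or endpoint. DLT evaluability has its own rule in SAP 7.3. SAP 11.5.10 also summarises cumulative dose and both durations and lists diary and accountability records, so a careful reader could rebuild the C1D1-based figure. That is right and limits the seriousness, but a published percentage should not need rebuilding before it can be read.

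Second, neither document states outright that the days between the run-in dose and C1D1 are dose-free, and the schedule tables and PK text are not in the public version. The gap is an inference. It is well supported by the single-dose wording, by the run-in dose being counted apart from Cycle 1, and by serial sampling to 72 hours, which would not give a single-dose profile if dosing continued.

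Third, actual dose intensity from first intake is a true mg/day figure, and the mismatch lies on the planned side. Keeping that duration and planning only the scheduled doses, 29*D*/(28 + *k*) per day for one cycle, also gives 100%. This is an equally valid repair, but it does not rescue the present formula.

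Fourth, some illustrations are extreme. The 100% score needs a QD patient who stopped after the run-in dose; a BID patient with one unit dose would score 50%. The 74.3% figure must not be read against the 75% DLT rule, which RDI does not enter.

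Finally, the imputation issue is separate, and nothing shows that last-dose dates will be missing. Where the recorded month equals the EOT month, a near-month error needs a last dose in the first days of that month. It stands as a secondary point only.

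**Conclusion.** The concern holds. As written, RDI understates dosing in every fully compliant patient who starts Cycle 1 and stays on the cohort dose. For QD the shortfall after one cycle is 6.5 to 17.1 points (100 − 93.5 and 100 − 82.9), falling to 1.2 to 3.4 points after six. For BID it is the same or slightly larger, depending on the run-in amount. This rests on the inferred dose-free gap and on reading Table 8 as 3 to 7 days from run-in dose to C1D1. Patients escalated under Protocol 6.6.1 are an exception: their planned figure stays at the cohort dose, so they can score higher.

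The damage is confined to the descriptive exposure summary, Table 14.1.3.9. It should be corrected because the measure fails its basic test and can rank patients in the wrong order. The last-dose imputation error is real when it applies, but its frequency is unknown.

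**What to change.** In SAP 11.5.10:
- Define actual dose intensity as the cumulative dose from C1D1 onward, run-in dose excluded, divided by the existing duration from C1D1. Keep RDI as that value over planned dose intensity.
- Report the run-in dose separately.
- Show RDI as not calculated for patients who never started Cycle 1.
- Footnote that patients escalated within the study can exceed 100%, because this change does not alter their planned dose.

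If the sponsor prefers to keep the duration from first intake, planned dose intensity must instead be built from the doses scheduled over that period.

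In SAP 11.3, for Cases 1 and 3 and the fallback, use the last documented intake from the diary or accountability records. If there is none, use the EOT date minus 30 days, kept within any recorded year and month, not before the record's start date and not after death.

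The cost is a wording change, one derivation and a small edit to the imputation rule. Both durations are already defined and the records are already collected.
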